Pain stressor challenge: the stressor challenge that will be used for this protocol consists of moderate levels of sustained deep muscular pain, achieved by infusing medication-grade 5% hypertonic saline into the relaxed masseter (jaw) muscle. Infusion is controlled by a computerized pump, through which participants maintain a pain intensity level of 40/100 via an electronic visual analog scale. Participants may experience physical or emotional discomfort during the challenge, however we will ensure that they are aware of the level of pain they will experience and that they understand the scale ratings of pain and internal states and can use them in a reliable manner.

Metformin/placebo side effects: metformin is in the biguanidine class of anti-diabetic drugs, and regulates hepatic gluconeogenesis, with secondary action enhancing glucose uptake at peripheral tissues through increased transport across the cell membrane. While metformin is not recognized as a true insulin sensitizing agent, it has been shown to improve insulin resistance and reduce fasting and postprandial insulin concentration, and has benefits over the thiazolidinedione class of drugs in terms of weight gain, improvements in lipid, vascular, and inflammatory profiles, and does not induce hypoglycemia even in non-diabetic individuals. Side effects of metformin include abnormal liver

changes, lactic acidosis and the more common side effects of gastric distress, nausea and vomiting. All subjects will be monitored for possible side effects such as nausea, vomiting, diarrhea, anorexia, and abdominal discomfort. These side effects tend to be mild, dose-related and improve with continued use of metformin. GI side effects will be minimized using a low dose of medication titrated slowly over a three-week period. Hypoglycemia is rare and tends to occur in the setting of alcohol abuse or prolonged starvation. Malabsorption of vitamin B₁₂ and folate occurs with long-term treatment, although it usually does not lead to anemia. Non-hormonal contraception will be recommended.

B) Discuss they the risks to the subjects are reasonable in relation to the anticipated benefits

Experimental work using imaging is essential for the advancement of knowledge in the field. This lays a rationale foundation for understanding the relationship between metabolic and mood disorders, the role of the endogenous opioid system in mediating that relationship, and the potential benefits of insulin-regulating or μ -opioid system-targeting treatments. The knowledge to be gained through these studies will also provide important objective information on the biochemistry and function of neurochemical systems in the human not obtainable by other means, and central to the study of metabolic dysregulation influences on affect/mood and novel avenues for intervention. Since risks to participants are of quite low order, we believe the gain of knowledge about the mood regulation effects of insulin metabolism outweigh these risks.

C) What are the benefits?

i. To the individual

There is no direct benefit to the participants in this project, except that the volunteers will have the benefit of being screened for insulin resistance. Patients will be informed that the medical significance of these studies is presently unknown, and the results will not influence their subsequent medical care. The risks to subjects participating in the project are minimal, as outlined above.

ii. To society

Experimental work using imaging is essential for the advancement of knowledge in the field. This lays a rationale foundation for understanding the relationship between metabolic and mood disorders, the role of the endogenous opioid system in mediating that relationship, and the potential benefits of insulin-regulating or μ -opioid system-targeting treatments. The knowledge to be gained through these studies will also provide important objective information on the biochemistry and function of neurochemical systems in the human not obtainable by other means, and central to the study of metabolic dysregulation influences on affect/mood and novel avenues for intervention. Since risks to participants are of quite low order, we believe the gain of knowledge about the mood regulation effects of insulin metabolism outweigh these risks.

11) Data & Safety Monitoring

a. *Will there be a board your study will report adverse events and other problems to?*

As this study does not constitute significant risk to patients through participation, a data monitoring board should not be required. All personnel involved with patients or their data will have formal training in human subjects protection and confidentiality. Subjects will not be identified in any reports or presentations generated by the study. All data will be kept confidential to the extent provided by local, state, and federal law. No identifiers will be kept with the data. New identification numbers will be assigned to each woman as she is recruited. This identification number will be used for the neuropsychological testing data, fMRI and PET scans. Images will be coded with this number. Those performing image analysis will be blind to subject information. Data collected during the performance of the studies is stored in mirrored RAID arrays which are both firewall-protected and isolated from access outside the immediate local network. The RAID arrays are backed up daily with digital tape. Failure of up to two drives in the RAID array does not result in the loss of data. RAID array drives are hot-swappable, and back-up drives are available in the event that individual drives may fail. Electronic data files in Excel or Word containing information about the study participants will be stored on password-protected drives, and separate from subject identifiers.

b. *Adverse Events*

i. Method of Identifying, Recording, Monitoring and Reporting Adverse Events

Adverse events are unlikely. If an adverse event should occur during PET scans, fMRI, blood draws, OGTT or neuropsychological testing, it would be expected to occur while the participant is in the presence of one of the investigators or their staff and the P.I. would be notified. Prior to the studies, volunteers will undergo physical exams to rule out the presence of undetected medical or psychological/psychiatric problems. During the performance of the studies, the volunteers will be monitored at all times by research personnel associated with the project (research assistant/associate, radiology technologists) or the investigators themselves. All the volunteers will have direct access to the phone numbers and pagers of the study coordinator and the responsible physicians, as well as a 24-hour contact number (emergency room services). These numbers are additionally included in the consent form provided to the volunteers. They will be informed of all the possible adverse events that could be encountered during the studies which may include, in very rare cases, allergic reactions to the radiopharmaceuticals, fatigue, thromboembolism, phlebitis and limb pain due to indwelling catheters, headaches or nausea. They will be encouraged to contact the investigators if they notice any symptoms of side effects. The investigators have ample prior experience in the utilization of the study protocols. All adverse events are immediately communicated to the IRB and the committee for human use of radioisotopes (RDRC/SHUR).

If the subject is having side effects of the metformin treatment they will have a contact number to reach the P.I. The P.I. will be reviewing all adverse events and they will be reported to the IRBMED committee and Health Science IRB regardless of severity or study relatedness, in compliance with the IRBMED Standard AE Guidelines. IRB Medical School definitions of severities (mild, moderate, severe), attribution, and expectedness will be used.

12) Statistical Design

PET imaging analysis: PET image data of 1) μ -opioid receptor BP_{ND} and 2) opioid release in response to stress challenge, calculated as the difference in BP_{ND} between baseline and challenge conditions, will be analyzed using Statistical Parametric Mapping software (SPM8, Wellcome Department of Cognitive Neurology, London, UK) with 1) volume-of-interest (VOI) analyses and 2) whole-brain statistical parametric mapping. VOIs will be defined using Montreal Neurological Institute (MNI) coordinates in affect/mood regulating regions (amygdala, nucleus accumbens, and rostral anterior cingulate). BP_{ND} values for these regions will be extracted for outlier assessment and further analyses in SPSS (SPSS Inc, Chicago, IL) or SAS (SAS Institute Inc, Cary, NC). In a separate set of analyses, whole-brain statistical parametric maps will be created for comparisons which do not assume selective involvement of specific regions, but will only include regions with specific μ -opioid receptor binding.

A global model based on the general linear model (GLM) will also be used to compare relationships between metabolic measures and mood/affective state, and to determine potential interactions and control for variables (e.g., age, BMI, estradiol and testosterone plasma levels) that could potentially confound the relationship between insulin resistance and mood state or opioid system activity.

6. Spinler SA. Challenges associated with metabolic syndrome. *Pharmacotherapy.* Dec 2006;26(12 Pt 2):209S-217S.
7. Hosler AS. Prevalence of self-reported prediabetes among adults participating in a community-based health awareness program, New York State. *Prev Chronic Dis.* Apr 2009;6(2):A48.

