Inclusion criteria: women aged 18-40, defined as metabolically healthy ($n = 18$) or insulin resistant ($n = 18$) based on insulin sensitivity (Si) values ("insulin resistance" defined as $Si < 1.61 \times 10^{-4}$; healthy as $Si > 1.89 \times 10^{-4}$ ($\text{min}^{-1} \times \mu\text{U}^{-1} \times \text{mL}^{-1}$); calculated by minimal model assessment of glucose tolerance test, based on the median of the non-diabetic population^{87,88}), and body mass index (BMI = weight (kg) / height² (m²)) between 18 kg/m² and 35 kg/m². Women with mild or moderate depressive symptoms not meeting the criteria for Major Depressive Disorder will be included.

Exclusion criteria: men, left handed, acute medical illness, uncorrected thyroid disease, diabetes (fasting glucose ≥ 126 mg/dL), neurological disease, major depression, substance abuse, claustrophobia or MRI contraindications (pacemakers, pumps, or metallic agents or devices), severe calorie restriction, intense physical exercise ≥ 1 hour/day, smoking within 6 months, hormonal, insulin sensitizing, or centrally acting medications within 2 months, pregnancy within 6 months, lactation, cardiac or pulmonary insufficiency, liver or renal insufficiency ($>2.5 \times$ normal transaminases levels, plasma creatinine ≥ 1.4 mg/dL), history of lactic acidosis, BMI ≥ 35 kg/m², and opioid allergy.

b. Recruitment Plan and Study Design

i. Number of Subjects

We plan to enroll 36 women aged 18-40, defined as metabolically healthy (n = 18) or insulin resistant (n = 18). We expect to perform initial clinical screening assessments on 60 women to achieve our target enrollment. We will replace drop outs with new subjects to complete studies on 36 subjects.

ii. Method of Contact

Women will be recruited through news boards, websites, UMClinicalStudies Registry, the Reproductive Endocrinology Clinics, and from the Investigational Weight Management study, a study of phenotypic influences on weight loss and metabolic function in normal and obese individuals, conducted by [name] at the Michigan Nutrition and Obesity Research Center (MNORC) in the Michigan Metabolomics and Obesity Center (MMOC). Participants enrolled in this study may choose to participate in the proposed project, and have been evaluated for general health, mood, physical fitness, body composition, and metabolic, metabolomic, and hormonal phenotyping.

iii. Method of Consent

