After an initial phone screen, a comprehensive written IRB approved consent form is mailed to the volunteer for her review. An appointment is made for further screening and review of study entry criteria. The investigators or research personnel will explain the nature of the study and answer the questions of the potential participant. If the subject qualifies and agrees to participate, she will sign a consent form.

iv. Method of Interaction/Procedure/Intervention

Insulin resistant women will be scheduled for up to 8 visits, and controls for 3 visits. Controls will not receive metformin and placebo treatments, and will not have repeat studies. Visits will be scheduled during the follicular phase of the menstrual cycle. Prior to all imaging procedures (PET and MRI), a urine pregnancy test will be administered. A description and summary of each visit is provided in the table below, followed by further experimental details:

Phone screening to determine initial eligibility to participate; schedule clinical screening & send review materials	
Details for each participant visit:	

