2	
Visit 2 will occur at the University of Michigan Functional MRI Laboratory, and will last approximately 2 hours.
 
Anatomical and functional MRI: to collect brain structural and anatomical T1-weighted images for PET image data processing and normalization, and to assess responses to words or images with an affective valence in comparison to neutral words or images. Scanning session may also include tasks of verbal and visual cognitive function. Prior to scanning, PANAS, POMS, and STAI will be administered to assess mood and affective state at time of scanning.

3	
Visit 3 will occur at the Nuclear Medicine Imaging Facilities in the University Hospital, and will last approximately 4 hours.

PET scan: to quantify endogenous μ -opioid receptors using the specific μ -opioid receptor radiotracer [^{11}C]carfentanil. The PET scan will consist of a baseline scan to assess baseline μ -opioid BP_{ND}, and a stress challenge scan, consisting of a 40 minute pain-free segment and a 20 minute pain stress challenge segment, to induce endogenous opioid release and receptor occupancy by the endogenous ligand(s). The challenge scan will allow assessment of presynaptic endogenous opioid function at μ -opioid receptors. Affective state will be assessed with PANAS at the beginning and end of each scanning segment. For cycling women, PET scans will be scheduled during the follicular phase of menstrual cycle..

Pain profile assessment: We will utilize a validated^{49,98} physical and emotional stressor, moderate levels of sustained deep muscular pain. An infusion profile will be developed in each subject that will maintain pain at a target 40 VAS units in a 0-100 scale, making it possible to draw comparisons between subjects and conditions for the same experiential stimulus.

End of study for metabolically healthy participants

Begin 1st treatment arm: insulin resistant participants randomized to 16 weeks metformin or placebo treatment.

Dosing: 500 mg metformin tablets or identically compounded placebo tablets orally after meals. Dosing schedule:

Week 1: 1 tablet after breakfast (500 mg daily dose)

Week 2: 1 tablet after breakfast and 1 tablet after lunch (1000 mg daily dose)

Week 3: 1 tablet after breakfast, after lunch, and after dinner (1500 mg daily dose)

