[name] will prescribe medication and supervise monitoring during treatment. If subjects have minor side effects, the dose escalation may be slower. Women will be maintained in the study if they can at least reach a dose of 1000 mg/day. Treatment will be monitored by phone calls to the subjects at 2 week intervals throughout each treatment arm.

Treatment will be coordinated through the Investigational Drug Services (IDS) in the University of Michigan Department of Pharmacy. IDS will manage treatment-related details including randomization and blinding, drug and placebo acquisition and compounding, medication storage and dispensing, treatment compliance, accountability records, and adherence to regulatory requirements.

4	Clinical (except histories, TSH, CCP, and blood count), anthropomorphic, and affect and mood assessments, similar to Visit 1.
5	PET scan, similar to Visit 3, but consisting of a single baseline PET scan without the stress challenge scan.
6	MRI scan, similar to Visit 2, may be performed depending on funding availability.

Four week medication-free wash-out period between treatment arms

Begin 2nd treatment arm: participants begin the 2nd arm of 16 weeks metformin or placebo treatment.

Dosing and medication details identical to those described for 1st treatment arm; *treatment will be coordinated through the IDS*

7	Clinical, anthropomorphic, and affect and mood assessments, similar to Visits 1 and 4.
8	PET scan, similar to Visits 5.
9	MRI scan, similar to Visit 2, may be performed depending on funding availability.

Clinical measures: clinical assessments of metabolic and endocrine environment to determine overall status at each of the time points and to assess response to treatment. Metabolic measures include a 2 hour 75g oral glucose tolerance test, with samples collected at -30, -15, 0, 30, 60, 90, and 120 minutes. Anthropomorphic measures will also be collected to control for changes in affective state that may be attributed to change in body composition. Sample collection and clinical assays will be performed at the MCRU and associated core laboratories.

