basis into tracer transport (K_1 ratio) and receptor-related BP_{ND} parametric maps, co-registered to each other. PET images will be co-registered to the T1-weighted MR structural, anatomical image, affine transformed and warped to standard MNI stereotactic space using mutual information algorithms¹⁰⁰. Inclusion of the pain challenge in a separate scan will allow comparison of pain and baseline conditions at the same timepoint in relation to tracer administration. The reduction in BP_{ND} from baseline to stress challenge provides a measure of endogenous opioid release in response to the stressor (related to the occupancy and endogenous ligand-receptor interactions)^{48,49}. The stress challenge scan will occur after the baseline scan to avoid carry-over effects from active to baseline states, as previously described^{50,101}.

MRI: structural, anatomical, and functional images will be acquired using a 3T whole-body magnetic resonance imaging scanner with a head coil. Images will be acquired axially with a three-dimensional, volumetric acquisition. Functional images will be collected during a presentation of words or images with an affective valence (positive or negative) or affectively neutral. Images may also be collected during validated tasks of verbal processing (women must decide whether presented words are written in upper or lower case letters, or if they have abstract or concrete word meaning) and visual memory (women must determine which of two test patterns matches the stimulus pattern).

Drug treatment: the University of Michigan Investigational Drug Service (IDS) will manage and coordinate metformin and placebo treatment. Metformin is the most widely prescribed drug for type 2 diabetes, and while generally not recognized as a true insulin sensitizing agent, it has been shown to improve insulin resistance and reduce fasting and postprandial insulin concentration without hypoglycemia. [name] will provide medical oversight and prescribe treatment medication. After baseline assessments, IDS will randomize participants to the order in which they receive metformin or placebo using a randomly permuted block design. Investigators and participants will be blinded to treatment order randomizations. Placebo pills will look identical to metformin pills but contain no active ingredients, and will be taken on an identical schedule as the active drug.

v. Survey Instruments

1. What are they?

- 1) Positive and Negative Affective Scale (PANAS)

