Potential subjects will be informed that becoming a participant in this study is entirely by their own free choice. Subjects may drop out of the project by their own free will, after having agreed to become a subject. They may refuse to enroll in this project, or drop out of this project without any penalty. By doing so, participants will not lose any benefits that they are entitled to. Subjects will be asked to discontinue their participation if they no longer meet criteria, did not comply or the investigator no longer thought it was safe for the subject to be involved with the study.

- ii. If a subject withdraws prior to completion, what is the plan for the use of their data

Subjects who have withdrawn prior to the completion of the study and have provided usable data in terms of the study's criteria will be included in the final analysis. Incomplete data sets which will not add any meaningful material for the research goals will not become part of the analysis.

8) Identifiable Data

- a. Indicate how subjects are identified in research records

Subjects will be indirectly identified in research records: personal identification (e.g. name, phone number, SSN, medical record number) will be replaced with coded identifiers in study databases. Coding will be kept secured and stored separately from study data.

- Explain the necessity for collection or maintaining data linked to subjects' identities.

Contact information for each will be collected and maintained in order to inform the subject of any necessary or pertinent information about the study prior to or following their participation. Also contact information such as mailing addresses are needed in order to mail the subject a packet of information about the study prior to their involvement. Name or medical record numbers may be used to confirm medical histories with subject permission.

- How long will the identifiers be retained?

Identifiers will be retained for 2 years following the final publications associated with the study, or when at least 2 years have elapsed since the formal discontinuation of the study.

9) Data Retention and/or Data Destruction Plan

- i. How long will you keep subject data?
- ii. If you plan to destroy the data, how will you destroy it?

Data collected will be retained for study recordkeeping purposes and for future research use. Data will be destroyed after 15 years by deleting the electronic files and shredding the paper documents.

10) Risks & Benefits

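### No pregnancy check is listed in the washout or before the first arm-2 dose, so a woman who conceives in the washout could start study drug while meeting an exclusion criterion

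*Combined protocol and SAP*

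**What the plan says.** The section on method of interaction, procedure and intervention gives the only pregnancy-testing rule in the text: "Prior to all imaging procedures (PET and MRI), a urine pregnancy test will be administered". It links testing to scans and not to dosing.

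The visit table sets the order for insulin-resistant women. The Visit 3 PET comes first, then "Begin 1st treatment arm: insulin resistant participants randomized to 16 weeks metformin or placebo treatment". After arm 1 come Visit 4 (clinical), Visit 5 (PET) and Visit 6 (MRI, if funded). The next line is "Four week medication-free wash-out period between treatment arms", and arm 2 begins directly after it. Visits 7, 8 (PET) and 9 (MRI, if funded) follow arm 2. On contact between visits the plan says: "Treatment will be monitored by phone calls to the subjects at 2 week intervals throughout each treatment arm".

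The exclusion criteria include "hormonal, insulin sensitizing, or centrally acting medications within 2 months, pregnancy within 6 months, lactation". The withdrawal section adds: "Subjects will be asked to discontinue their participation if they no longer meet criteria". The paragraph on metformin and placebo side effects closes with: "Non-hormonal contraception will be recommended".

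**The concern.** The participants are women aged 18 to 40 who may not have used hormonal medication within 2 months of entry. Pregnancy is an exclusion, and the withdrawal rule carries eligibility past entry. The plan therefore intends that a woman who becomes pregnant should stop, but it lists no step that would show a pregnancy before arm-2 drug is started.

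The two arms differ here. Arm 1 starts after a PET visit that carries a test. Arm 2 starts after a drug-free interval that carries none. The imaging-only rule happens to place a test just ahead of the first arm in the table but not the second.

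What is at stake is participant protection and adherence to the protocol's own criteria: study drug, which may be metformin, could be given to someone whom those criteria would stop. No estimand, test or sample size is affected.

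**Working it through.** The plan states no test age or pregnancy risk, so there is no figure of its own to reproduce. The check is a timeline followed by an illustrative count.

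**Inputs from the documents:** 4-week washout; 16 weeks per arm; tests before PET or MRI only; calls every 2 weeks within each arm; 18 insulin-resistant women.

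**Assumptions, not in the documents:** annual pregnancy risk of 5% to 20%, spread evenly over time; a urine test detects only conceptions at least 2 weeks old; about 9 of the 18 women take metformin in arm 2. On the last, the plan says "IDS will randomize participants to the order in which they receive metformin or placebo using a randomly permuted block design" but gives no ratio.

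**Age of the last test at the first arm-2 dose**

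Age = 4-week washout + weeks from the scan to the last arm-1 dose (negative if the scan comes after that dose).

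- Scan on the day of the last dose: 4 + 0 = 4 weeks.
- Scan 1 or 2 weeks before the last dose: 4 + 1 = 5, or 4 + 2 = 6 weeks.
- Scan 1 or 2 weeks after the last dose, washout counted from that dose: 4 − 1 = 3, or 4 − 2 = 2 weeks.

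Tests, visits and calls listed in the washout or at arm-2 start: none. The next listed test precedes the Visit 8 PET, about 4 + 16 = 20 weeks after a test done at the end of arm 1.

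**Washout conceptions that a test at arm-2 release could detect**

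These are conceptions in the first 2 of the 4 washout weeks. Per woman, p = 1 − (1 − r)^(2/52), where r is the annual risk.

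- r = 5%: p = 1 − 0.95^(2/52) = 0.197%.
- r = 20%: p = 1 − 0.80^(2/52) = 0.855%.

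Among 18 women:

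- Expected number, 18p: 0.035 to 0.154, that is 0.04 to 0.15.
- Chance of at least one, 1 − (1 − p)^18: 3.5% to 14.3%.

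Among about 9 women on metformin in arm 2:

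- Expected number, 9p: 0.018 to 0.077, that is 0.02 to 0.08.
- Chance of at least one, 1 − (1 − p)^9: 1.8% to 7.4%.

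Conceptions in the last 2 washout weeks, about half of all washout conceptions under even spacing, would be too recent for the release test. Neither these nor conceptions during treatment are counted above; finding them depends on the missed-period question.

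**The case against.** The strongest objection concerns how firm the timing is. A reader might take 4 weeks as a documented minimum age for the last test. The documents do not support that. They give no day for Visits 5 and 6 relative to the last arm-1 dose. The PET imaging paragraph describes these scans as following the treatment arm, and follicular-phase scheduling may move them. The washout is defined only as free of medication. A scan one or two weeks into it is possible, and the test would then be 2 to 3 weeks old. This objection stands, and the figure is given here as about 4 weeks on table order. It does not remove the gap, because no test is listed at arm-2 release on any of these timings.

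A reader might also infer that the first arm-2 call must come after dosing has begun. Only the 2-week interval is stated, so a call on the first day fits equally well. Even then, the plan says nothing of asking about pregnancy.

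Next, the text is incomplete. The part just before the eligibility criteria and the consent pages are not in the text supplied, and the drug service handles dispensing and regulatory adherence under a supervising prescriber. A check may already exist. That limits the claim to what is listed, and if so only the record needs changing.

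The pregnancy rates are outside assumptions, and the count ignores cycle-based scheduling. Recruitment includes reproductive endocrinology clinics, and the table refers to cycling women as if some may not be, so fertility in this group is unknown. The release test also covers only about 2 weeks of washout conception time, roughly 10% of the 20 weeks between listed tests (2/20). All of this stands and keeps the point small.

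Finally, every radiation exposure is preceded by a test, contraception is recommended, and women have direct access to study physicians. These are real safeguards, but none is a check before arm-2 dosing.

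**Conclusion.** The point holds as a minor safety improvement. On the supplied text, the last listed pregnancy test is about 4 weeks old at the first arm-2 dose (plausibly 2 to 6 weeks, depending on when the scan falls). Nothing listed between that test and the dose would reveal a pregnancy. A woman who conceives in the washout could start study drug while meeting an exclusion that the plan carries forward through its withdrawal rule.

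The expected yield of a release test is well below one case: 0.04 to 0.15 among 18 women, conditional on the assumed pregnancy risk and detection limit. The argument rests on low cost and consistency with the plan's own criteria, not on frequency.

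A reader might infer that the plan exposes pregnancies to a known hazard of metformin, or that the crossover comparison is compromised. The documents support neither. They name no fetal risk of metformin, and the missing check alters no analysis.

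**What to change.** Require a negative urine pregnancy test, the kind already used before imaging, before arm-2 study drug is released. Add a missed-period question to the planned 2-weekly calls in both arms, with a urine test if a missed period is reported. The question is less informative for women who do not cycle regularly, so it should supplement the release test and not replace it.

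The cost is about 18 extra urine tests, one per insulin-resistant woman, and one added question per call. A positive test would trigger the existing withdrawal rule; it would not recover that woman's second-period data. If the drug service already tests at dispensing, conduct need not change, and one line in the visit table between the washout and arm 2 would record it.

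### Dose steps are a week apart but the described calls are two weeks apart, so on the default schedule one of the two steps has no scheduled tolerability check

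*Combined protocol and SAP*

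**What the plan says.** The relevant text is in section iv (Method of Interaction/Procedure/Intervention), in the visit table under the first treatment arm.

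- **Dose steps.** Week 1 is one 500 mg tablet daily. Then: "Week 2: 1 tablet after breakfast and 1 tablet after lunch (1000 mg daily dose"). Then: "Week 3: 1 tablet after breakfast, after lunch, and after dinner (1500 mg daily dose").
- **Slowing rule.** "If subjects have minor side effects, the dose escalation may be slower". A woman stays in the study if she can reach at least 1000 mg daily.
- **Scheduled contact.** "Treatment will be monitored by phone calls to the subjects at 2 week intervals throughout each treatment arm". The day of the first call is not given. The next listed visit (visit 4) comes after the arm.
- **Supervision.** A study clinician "will prescribe medication and supervise monitoring during treatment".
- **Second arm.** "Dosing and medication details identical to those described for 1st treatment arm".
- **Blinding** (section iv, Drug treatment). "Investigators and participants will be blinded to treatment order randomizations".
- **Side effects** (section 10, Metformin/placebo side effects). "All subjects will be monitored for possible side effects such as nausea, vomiting, diarrhea, anorexia, and abdominal discomfort". That section describes these effects as mild, related to dose and easing with continued use. It relies on slow titration over three weeks to limit the gastrointestinal ones.
- **Reporting routes** (section 11, Adverse Events). Women have a number to call about metformin side effects and direct phone and pager access to the coordinator and responsible physicians. They are encouraged to report symptoms. Section 10 adds a 24-hour emergency number.

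**The concern.** The slowing rule can act only if somebody knows about symptoms before the next tablet is added. The dose changes only in the first weeks of an arm, and it changes faster than the calls come round. A woman with nausea or gastric distress who does not phone in would move up by default at a step that a short call could have delayed.

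What is at stake is tolerability during titration. Both arms use the same schedule, but each woman takes active drug in only one of them, so each has a single metformin titration.

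**Working it through.** The plan states no figure to reproduce. The check is a calendar comparison.

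**Inputs** (all from the visit table in section iv). Day 1 is the first tablet. The 500 mg dose covers days 1 to 7, the 1000 mg dose covers days 8 to 14, and 1500 mg starts on day 15. Calls are 14 days apart. An arm lasts 16 × 7 = 112 days.

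**Rule.** A step counts as checked if a scheduled call falls while the woman is on the dose she is about to leave: days 1 to 7 for the step to 1000 mg, and days 8 to 14 for the step to 1500 mg.

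**General result.** The two windows are adjacent and together span 7 + 7 = 14 days. Calls 14 days apart put at most one call in any 14 consecutive days. Both windows therefore cannot contain a call.

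**By day of first call, d** (later calls at d + 14, d + 28, and so on):

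| First call | Next call | Check on 500 mg | Check on 1000 mg |
|---|---|---|---|
| days 1–7 | days 15–21 | yes | no |
| days 8–14 | days 22–28 | no | yes |
| day 15 | day 29 | no | only if the call comes before the added dinner tablet |

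**Edge case.** If a same-day call before the added tablet is allowed to count, calls on day 1 and on day 15 before dinner nominally cover both steps. A call on the day of the first tablet says almost nothing about tolerability. Setting it aside is a clinical judgement, not a calendar fact.

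**Calls per arm now.** The number is floor((112 − d)/14) + 1.
- d = 1: floor(111/14) + 1 = 7 + 1 = 8.
- d = 14: 98/14 + 1 = 7 + 1 = 8.
- d = 15: floor(97/14) + 1 = 6 + 1 = 7.

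**After the change.** Calls on day 7 and then days 14, 28, …, 112 number 1 + 8 = 9. Day 7 lies in the first window and day 14 in the second, so 2 of 2 steps are checked.

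**Extra calls.** Per woman per arm, 9 − 8 = 1 to 9 − 7 = 2. For 18 women over two arms, 1 × 18 × 2 = 36 to 2 × 18 × 2 = 72.

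**The case against.** The best defence is that the protocol breaks no rule of its own. The slowing rule is permissive and triggered by symptoms, and nothing makes a step conditional on a scheduled call. Nausea and gastric distress are felt by the woman herself, and a call would also depend on what she says. Section 11 encourages her to report and gives her the means to do so. The effects are described as mild, and titration is already gradual.

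Most of this stands and keeps the point small. It does not remove it: none of those safeguards is tied to a dose step, and the calls are the monitoring for which the visit table gives a timetable.

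Three stronger readings are tempting, and the documents do not support them.

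- *Both steps go unchecked.* This needs a first call on day 15 after the added tablet, or later still. A first call on days 16 to 21 would leave more than two weeks without contact, which fits poorly with 2-week intervals throughout the arm. On the ordinary reading, the step to the full dose is checked.
- *The calls are the only scheduled contact.* The available text describes no other contact during titration. However, a part of the protocol before the eligibility criteria could not be checked, and the timing of the pharmacy service's dispensing and compliance contacts is not given.
- *The plan contradicts itself, or the trial's results are affected.* The call interval and the slowing rule can both be followed as written. The documents give no rate of symptoms or of non-reporting from which an effect on dropout, endpoints or power could be derived.

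**Conclusion.** The point holds as a cheap improvement. On the default schedule, and with the contacts described, one of the two dose steps lacks a meaningful scheduled tolerability check. With a first call at about day 14 it is the step from 500 to 1000 mg; with a first call in week 1 it is the step to 1500 mg. Before that step, slowing rests on the woman's own report and on monitoring with no stated timing.

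The conclusion assumes that escalation follows the weekly default, that no further titration contacts are set out elsewhere, and that a call on the first day of dosing is not a useful check. The number of women affected cannot be estimated from the documents.

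**What to change.** In both arms, add a call at about day 7 and fix the first 2-weekly call at about day 14, each before the next tablet is added. At each call, ask about side effects and tell the prescriber of any symptoms before the step. Then continue every 2 weeks. If escalation is slowed, keep one call before each remaining step. A day-21 call on the full dose is optional.

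Use the same schedule in both arms, because a different one could reveal treatment order. Dose levels and the threshold for slowing stay with the trial's clinicians.

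**Cost.** A short amendment, and 9 calls per arm in place of 7 or 8: 1 to 2 extra short calls per woman per arm, about 36 to 72 in total. Each replacement woman treated in both arms adds 2 to 4 (1 × 2 to 2 × 2). The optional day-21 call would add 1 × 18 × 2 = 36. Calls added because escalation is slowed are not counted. Symptoms would need to reach the prescriber promptly, within about a day. The protocol does not say who makes the calls; it is assumed that the same people can make the extra ones. No new visits are needed.
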